### **8.3.1.3 Engraftment**

Engraftment of transduced cells will be assessed using vector gene marking in granulocytes, PBMC, CD3, CD34, CD19 and myeloid progenitor cells. Any assessments in which the result indicates that cells were not detected, will be assigned a value of 0.

The vector copy numbers in each type of cell will be summarised for IMP treated subjects by visit using descriptive statistics. In addition, for each cell type, plots of the median and range for copy numbers over time on a logarithmic scale will be produced along with individual subject plots.

### **8.3.1.4 Cellular and Humoral Immune System Recovery**

Immune reconstitution will be assessed using lymphocyte subsets. Absolute numbers and percentages of CD3+, CD4+, CD8+ CD4+CD45RA+CD27+ T-lymphocytes, CD19+ B-lymphocytes and CD16+CD56+ NK cells will be measured.

For each of the lymphocyte subsets, the actual values and change from baseline will be summarized by visit for each of the IMP treated groups using descriptive statistics. The median value and range will be plotted by treatment group over time on a logarithmic scale and individual counts will be plotted along with the age-dependent normal ranges provided by the study site.

In addition, statistical testing of the change from baseline to 6 and 12 months will be performed for the IMP treated subjects. If the difference is normally distributed, a paired t-test will be used. Otherwise, the Wilcoxon signed rank test will be used.

The trend over time in the IMP treated subjects will be examined for each count separately, using mixed models for repeated measures (MMRM) with visit and baseline count as fixed effects, and subject as a random effect, utilizing the compound-symmetry covariance structure. If counts are approximately normally distributed they will be analysed on the original scale. Otherwise, if log transformation can normalize the data, statistical analysis will be performed on log-transformed data. If the data are still not normal, the data will be ranked in ascending order of magnitude and the analysis will be performed on the ranks.

### **8.3.1.5 RBC ADA Enzyme Activity and Reduction in dATP**

RBC ADA enzyme activity, dATP and plasma deoxyadenosine will be summarized by visit for each of the IMP treated groups using descriptive statistics. The median value and range will be plotted by treatment group over time on a logarithmic scale. In addition, individual subject plots will be created.

Changes from baseline in each of the parameters will be calculated with baseline being the pre-treatment evaluation. The change from baseline will be summarized by visit for each of the IMP treated and HSCT control groups (data permitting) using descriptive statistics and 95% confidence intervals.

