### **3.2.2 ADA enzyme replacement therapy**

The toxic compounds that accumulate in ADA deficiency (dATP) cross the cell membrane poorly but are metabolised to ADA substrates (dAdo) that rapidly equilibrate with plasma via the nucleoside transporter. Thus maintaining sufficient levels of circulating 'ectopic' ADA either in the plasma or in a population of cells can normalise metabolite levels in enzyme deficient cells. This was initially demonstrated by the use of repeated red cell transfusions for the treatment of ADA deficiency (Polmar, 1978). Metabolic and immunological correction was seen but the effects were transient and outweighed by the risk of viral transmission and iron overload.

PEG-ADA is a bovine form of ADA conjugated to polyethylene glycol. The covalently bound PEG is intended to prevent proteolysis and uptake by cells and to prolong circulating life and reduce immunogenicity. PEG-ADA has been used since 1987 for the treatment of ADA-SCID patients who lacked a genetically identical donor (reviewed in (Hershfield, 1995a; Hershfield, 1995b). PEG-ADA avoids the risks of red cell transfusion and the amount of enzyme activity provided is equivalent on a ml to ml basis to ~1800 times the ADA activity of packed erythrocytes. Three mls of PEG-ADA contains the ADA equivalent of ~10^12 T lymphocytes. The preparation is given as an intramuscular injection at ~30 u/kg on a weekly basis.

[figure not shown]
Data on long term follow up of immunologic function and outcome in PEG-ADA treated patients has been limited since there has been no central point for data collection. However a recent review (Gaspar et al., 2009) has highlighted outcomes in over 185 patients treated with

PEG-ADA until September 2008 (about 90% of those ever treated). PEG-ADA has been used as initial therapy for patients who lacked a related HLA-identical donor, when assessment of risk and benefit by physicians and parents favoured Enzyme Replacement Therapy (ERT) over other options (Hershfield, 2004; Booth et al., 2007).

Overall, 70% of patients treated with PEG-ADA began ERT at <1 year of age (50% were <6 months old). Half of the remaining patients started treatment at 1-3 years of age, and half at 3-34 years of age. Many of these latter “delayed” or “late” onset patients had pulmonary disease or other consequences of chronic immune deficiency, which made them poor candidates for partially mismatched HSCT with conditioning.

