### **4.3 Study endpoints**

#### **4.3.1 Primary endpoints**

- To assess survival at 1 year for patients treated with IMP.
- To assess event free survival at 1 year for patients treated with IMP.
  - To compare survival and event free survival at 1 year for patients treated with IMP compared to patients treated with allogeneic HSCT.
- Success of engraftment of transduced cells as assessed by vector copy number in the cells at each study visit.
- Reconstitution of cell mediated and humoral immunity as assessed by evidence of changes in T cell number, function and circulating immunoglobulin levels at each study visit.
- Correction of metabolic abnormalities as assessed by dATP and evidence of ADA activity in erythrocytes at each study visit compared to published data from HSCT treated patients

The following will be analysed at a specialist laboratory in Germany and the results reviewed and interpreted by the PI and the study team.

- Analysis of frequency of vector integration into known proto oncogenes
- Analysis of frequency of clonal expansion associated with vector integration near proto oncogene

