### **8.2.2 Post-infusion monitoring**

Patients will be monitored on protocol at 1 month, 6 weeks, 3, 6, 9, 12, 18, 24, 30 and 36 months post-infusion. Window to carry out these visits is +/- 5 days for visits at 1 month, 6 weeks and +/- 2 weeks for visits at 3, 6, 9, 12, 18, 24, 30 and 36 months. Follow-up as part of the routine clinical care of post-transplant patients will be annual after this.

Monitoring, testing being performed and information to be collected on CRF are fully detailed in Appendix 5. Modifications to this protocol will be adopted as necessary to improve sample-processing capability, and a degree of flexibility regarding the actual dates of assessment will be maintained. Additional tests may be carried out in the event of a significant adverse effect to ensure optimal clinical care.

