### **9.1.4 Bone marrow harvest**

Bone marrow will be harvested from the patient under general anaesthesia from the posterior iliac crests on both sites by multiple punctures. Marrow will be collected into sterile bags containing ACD (acid citrate dextrose) (Baxter). The amount of marrow collected will be equivalent to 20 ml/kg of body weight. The risks of the procedure include the standard risks of general anaesthesia and complications associated with the bone marrow harvest procedure. The latter include pain at the site of puncture following the procedure, excessive blood loss resulting in anaemia and the potential for infection at the puncture site. The anaesthetic risks will be minimised by the anaesthetic being administered by a paediatric anaesthetist at a major paediatric tertiary referral centre. The patient will be given paracetamol pain relief after the

procedure and will be monitored carefully to check haemodynamic status. It is likely that the patient will need a blood transfusion after the bone marrow harvest. Infection risk will be minimised by careful cleansing of the site prior to needle insertion and strict adherence to sterile technique during the procedure.

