## 5 Endpoints

### 5.1 Primary Endpoints

Primary endpoints for this study are:

- Overall survival at 1 year for patients treated with IMP.
- Event-free survival at 1 year for patients treated with IMP.

- Vector copy number in the cells at each study visit.
- Changes in T cell number, function and circulating immunoglobulin levels at each study visit.
- dATP and ADA enzyme activity in erythrocytes at each study visit.

The following endpoints will be analysed at a specialist laboratory in Germany and the results will be reviewed and interpreted by the PI and the study team, so these will not be included in this Statistical Analysis Plan (SAP).

- Frequency of vector integration into known proto oncogenes.
- Frequency of clonal expansion associated with vector integration near proto oncogene.

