### **8.4.2 Concomitant Medications**

Concomitant medications taken during the study will be listed.

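### Red-cell ADA activity is summarised at every visit with no handling of red-cell transfusion, so donor cells can raise the month 1 and week 6 values

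*SAP*

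**What the plan says.** Protocol 4.3.1 lists among the primary endpoints "Correction of metabolic abnormalities as assessed by dATP and evidence of ADA activity in erythrocytes at each study visit", and SAP 5.1 repeats it as "dATP and ADA enzyme activity in erythrocytes at each study visit". Protocol 8.1.2 treats these assays as the measure of how well gene therapy has corrected the metabolic phenotype. The visits start early; Protocol 8.2.2 states "Patients will be monitored on protocol at 1 month, 6 weeks, 3, 6, 9, 12, 18, 24, 30 and 36 months post-infusion". The schedule (Protocol Appendix 5, SAP 3) takes the metabolic sample before treatment and at every one of these visits.

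The analysis is in SAP 8.3.1.5: "RBC ADA enzyme activity, dATP and plasma deoxyadenosine will be summarized by visit for each of the IMP treated groups", by descriptive statistics. That section adds medians and ranges over time, individual subject plots, and change from the pre-treatment value with 95% confidence intervals. It does not mention transfusion.

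The protocol does mention it. On marrow harvest, section 9.1.4 says "It is likely that the patient will need a blood transfusion after the bone marrow harvest". On the principle that circulating ADA can normalise metabolites, section 3.2.2 says "This was initially demonstrated by the use of repeated red cell transfusions for the treatment of ADA deficiency"; it adds that correction was seen but did not last.

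Nothing elsewhere in the SAP closes the gap. The schedule has no transfusion item. If transfusions are recorded as concomitant treatment, SAP 8.4.2 provides only that "Concomitant medications taken during the study will be listed". The sensitivity analyses in SAP 8.3.4 depend on major protocol violations and cover survival, lymphocyte subsets and engraftment, not the metabolic endpoint.

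**The concern.** The assay reads ADA in whatever red cells are in the sample. After a transfusion some of these are donor cells with their own ADA, and the by-visit summary cannot separate them from gene-corrected cells. A child with no engraftment could show red-cell ADA well above the untreated level at the first visits, and the mean, median, change from baseline and confidence interval would all take that in. A transfusion before the pre-treatment sample would work the other way, by raising the baseline.

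There are 10 on-study subjects (SAP 7.1), so a few transfused children can move a visit summary. The 6-month interim look reports all available data (SAP 6). Of the four post-infusion visits up to then, two are clearly exposed and a third may be. An early rise could be read as rapid metabolic correction.

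**Working it through.** The plan states no sample size, power or target for this endpoint, so there is no figure of its own to reproduce. The check is how much red-cell ADA donor cells alone could contribute.

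Inputs from the documents:
- Marrow volume harvested: 20 ml/kg (Protocol 7.5.2, 9.1.4).
- Harvest day: day -2 for marrow (Protocol 7.5.1).
- Visits: month 1, week 6, month 3, month 6 (Protocol 8.2.2).
- Benchmark: ADA activity below 3% for enzymatic diagnosis (Protocol 5.1.1). It is used here only for scale; the SAP applies no threshold.

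Assumptions not in the documents: blood volume 75 ml/kg; the harvest replaced volume for volume with blood of similar red-cell content; donor cells with 100% of normal ADA and the child's own cells with none; donor cells of uniform age, so that they are lost linearly over a lifespan L; no engraftment.

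Formula: donor share at day t = f0 × max(0, 1 − (t − t_tx)/L), where f0 is the share just after transfusion and t_tx is the transfusion day. The share approximates the percentage of normal red-cell ADA due to donor cells.

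Harvest fully replaced, L = 120 days:
- f0 = 20/75 = 26.7%.
- Month 1 (day 30): 26.7% × (1 − 32/120) = 19.6%.
- Week 6 (day 42): 26.7% × (1 − 44/120) = 16.9%.
- Month 3 (day 91): 26.7% × (1 − 93/120) = 6.0%.
- Month 6: zero, because more than 120 days have passed.

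The ranges below use f0 from 10% to 40%, L from 80 to 120 days, and visit days 30.4, 42, 91.3 and 182.6.

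| Scenario | Month 1 | Week 6 | Month 3 | Month 6 |
|---|---|---|---|---|
| Harvest fully replaced, L = 120 | 19.6% | 16.9% | 6.0% | 0 |
| Half replaced, L = 120 | 9.8% | 8.4% | 3.0% | 0 |
| Transfusion on day -2, ranges | 5.9–29.2% | 4.5–25.3% | 0–8.9% | 0 |
| Transfusion on day +14 or +28, ranges | 8.0–39.2% | 6.5–35.3% | 0.3–18.9% | 0 |

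Month 1 and week 6 exceed 3% in every scenario. Month 3 after a harvest transfusion does not always do so:
- L = 120: f0 must be at least 3%/(1 − 93.3/120) = 13.5%.
- L = 100: f0 must be at least 3%/(1 − 93.3/100) = 44.8%, outside the range used.
- L = 80: no donor cells remain.

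Month 6 is touched only by a transfusion after about day 182.6 − 120 = 63.

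**The case against.** The strongest objection concerns reach. Marrow harvest is the fallback; leukapheresis is preferred (Protocol 7.5.2), and transfusion is called likely only after marrow harvest. For leukapheresis, Protocol 9.1.5 gives a possible blood loss of 100 to 200 ml, to be kept as low as possible, and does not mention transfusion. A reader might infer that nearly every child will be transfused after busulfan. The anaemia rate of 88% in Protocol Appendix 6 comes from adult label data; the paediatric text there gives no such rate, and no transfusion plan is stated. This objection stands: the bias applies to transfused children, whose number the documents do not give.

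A reader might also infer that donor cells would produce a spurious fall in dATP. The documents do not support that with confidence. PEG-ADA continues to about one month after infusion (Protocol 7.5.8), and Protocol 3.2.2 says circulating ADA can itself normalise metabolites. In children already on PEG-ADA, both baseline and month 1 dATP reflect it. After withdrawal, the earlier patient described in Protocol 3.2.4.4 had a rise in red-cell dATP. No dATP effect has been computed here. Red-cell ADA activity is the clearer case, since the PEG coating is meant to prevent uptake by cells (Protocol 3.2.2).

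Finally, the analysis is descriptive, and vector copy number is a separate primary endpoint. Failure of engraftment or T-cell recovery is assessed at 180 days (Protocol 8.3). A child without engraftment would not go undetected because of this. That limits the consequence, but it does not correct the early red-cell ADA summaries.

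**Conclusion.** The point holds for red-cell ADA activity at month 1 and week 6 in transfused children. Following SAP 8.3.1.5 as written can give values biased upward for a primary endpoint, by a mechanism the protocol itself describes. For a harvest transfusion the donor contribution is 5.9% to 29.2% of normal at month 1 and 4.5% to 25.3% at week 6. These figures rest on the assumed donor share, red-cell lifespan and normal donor activity.

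It would go too far to say that all results from month 1 to month 3 are compromised: month 3 ranges from 0 to 8.9% after a harvest transfusion and depends on lifespan. From month 6 there is no effect without later transfusion. The point does not bear on overall or event-free survival. It is a cheap improvement to the SAP and does not undermine the trial's metabolic conclusion, provided that conclusion rests on the later visits.

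**What to change.** In SAP 8.3.1.5 and the data collection:
- Record the date of every red-cell transfusion, including any before the pre-treatment sample. The concomitant-treatment record starts only at the Treatment column of the schedule, so it cannot supply those earlier dates.
- Flag red-cell ADA and dATP samples taken within 120 days after a transfusion.
- Keep all samples in the main by-visit table. Restricting the main table to unflagged samples would select, among 10 children, those who needed no transfusion.
- Add a pre-specified sensitivity table and plots without flagged samples, and mark flagged points on the individual plots.
- If the baseline sample is flagged, omit that child's change from baseline in the sensitivity table. Do not substitute the diagnostic value: enzymatic diagnosis precedes PEG-ADA, so this would mix untreated with on-treatment baselines, and a child diagnosed by sequencing may have no such value.
- Apply the flag to HSCT controls only where transfusion dates exist, and say where they do not. Such dates are not among the items listed in Protocol Appendix 8.
- Rest the conclusion on metabolic correction on month 6 onward.

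The cost is one added data field, one derived flag and one extra set of outputs. The downside is fewer values at the early visits in the sensitivity table. This is data handling only and changes nothing in clinical care.

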#### **3.2.4.4 PEG-ADA withdrawal leads to proliferation of gene transduced cells**

The use of PEG-ADA has always clouded the issue of whether these early trials were successful in correcting immune function and it has always been felt that only complete withdrawal of replacement therapy would answer this question. To date two patients from two different studies have undergone elective withdrawal of PEG-ADA. Kohn et al. at Children's Hospital Los Angeles (UCLA) attempted withdrawal in one patient from their cord blood gene transfer program. Over two months of observation, there was a 30-100 fold increase in the proportion of gene transduced T cells. However, there was an overall 25% decrease in the total numbers of T cells and a decrease in the B and NK cell numbers. This prompted investigators to restart PEG-ADA and the patient remains on enzyme replacement to this day (Kohn et al., 1998).

A patient from the Milan study also stopped PEG-ADA on the grounds that there was a plateau in immune function and the investigators reasoned that stopping PEG-ADA may provide an advantage to transduced cells (Aiuti et al., 2002b). The discontinuation of PEG-ADA led to a selective growth advantage of gene transduced T lymphocytes as assessed by PCR quantification, fluorescence in situ hybridisation and T cell clonal analysis. Transduced cells expressing the ADA vector increased during PEG-ADA withdrawal eventually replacing the non-transduced T cell population, reaching nearly 100% of circulating lymphocytes. Absolute T cell counts increased and stabilised to levels significantly higher than those observed during PEG-ADA treatment. Functional immunological parameters also improved with demonstration of vaccine specific responses and responses to the  $\phi$ X174 neoantigen. Intracellular PBL ADA activity also increased by 1 log and persisted at approximately 50% of normal individuals (which is in the range for immunologically normal heterozygote parents) but there was a rise

in the red blood cell dATP levels suggesting that the total mass of gene corrected lymphocytes producing ADA was not sufficient for systemic detoxification. Nevertheless this patient has remained off PEG-ADA and is clinically well. It has not been reported whether prophylactic medication has been discontinued.

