#### 7.5.8 Discontinuation of PEG-ADA one month after infusion of gene modified cells

PEG-ADA will be continued until one month (+/- 6 days) post-infusion of gene-modified cells. PEG-ADA will be restarted if i) the child is withdrawn from the study ii) if after 180 days there is no evidence of gene modified cell engraftment and/or failure of T cell recovery.

PEG-ADA may be restarted at PI's discretion prior to this time point on clinical grounds e.g. infective problems or delayed T cell reconstitution. In instances when PEG-ADA has been restarted, PEG-ADA may be withdrawn again, if the patient remains well and meets withdrawal criteria (i.e. has detectable PBSC ADA activity and/or detection of gene modified cells above baseline levels).

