### **8.2.1 Pre-treatment investigations**

Pregene therapy visit will be carried out prior to gene therapy. This visit will include pre-treatment monitoring investigations, which should be carried out within 3 months of the start of gene therapy treatment according to Appendix 5

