#### **9.1.2 Infection**

Withdrawal of PEG-ADA can have adverse effects on immunity, as well as on other organ systems. Once PEG-ADA is withdrawn, the numbers of circulating T, B, and NK lymphocytes will decline and may remain low for several months until the autologous transplant of gene-corrected CD34+ cells leads to immune reconstitution. It is possible that a severe infection may develop during this time and this could even be fatal if it does not respond to therapy. If immunity is severely decreased after discontinuation of enzyme replacement therapy and the subject experiences multiple or serious infections, then therapy may have to be resumed.

It is also possible that the cells for infusion could become infected with bacteria or fungus during the growth period in the laboratory. If there is any evidence of infection of the cells with unwanted agents and busulfan has already been administered, the cells will be returned to the subject with appropriate antibiotic cover. If the infection significantly affects viability (to a total cell dose of  $<0.5 \times 10^6/\text{kg}$ ) then transduced cells will not be returned and the back-up

bone marrow will be infused. However, there is a remote chance that subjects could acquire a bacterial or fungal infection from the re-infused cells (this also applies to the back-up cells, if administered).

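### The IgG, dATP and lymphocyte summaries take no account of immunoglobulin-replacement or PEG-ADA status, so pooled IgG cannot be read as humoral recovery and the other changes lack a label for what they are measured against

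*SAP*

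**What the plan says.** For the metabolic parameters, SAP 8.3.1.5 states: "Changes from baseline in each of the parameters will be calculated with baseline being the pre-treatment evaluation". It continues: "The change from baseline will be summarized by visit for each of the IMP treated and HSCT control groups (data permitting", so the HSCT part is conditional on data.

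SAP 8.3.1.4 summarises lymphocyte values and changes by visit and adds that "statistical testing of the change from baseline to 6 and 12 months will be performed for the IMP treated subjects". Its mixed model contains visit, baseline count and subject. The last paragraph of SAP 8.3.2.2 summarises IgG, IgA and IgM, and their changes, by visit for the gene-therapy subjects. None of these passages mentions PEG-ADA or immunoglobulin replacement (IgRT) status. SAP 5.1 makes circulating immunoglobulin part of a primary endpoint.

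On timing, Protocol 8.2.1 describes the pre-treatment tests as ones "which should be carried out within 3 months of the start of gene therapy treatment". Protocol 7.5.8 says: "PEG-ADA will be continued until one month (+/- 6 days) post-infusion of gene-modified cells". Protocol 3.1.6 has immunoglobulin started once the diagnosis is made, and Protocol 5.4 leaves it unchanged by study entry. A footnote to the immunoglobulin row of the schedule (SAP 3, Protocol Appendix 5) lets an assay already done at diagnosis stand in for the pre-gene-therapy assay.

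**The concern.** Both background therapies act on the quantities being summarised. Infused immunoglobulin is measured as IgG. Circulating ADA lowers metabolites (Protocol 3.2.2), and Protocol 9.1.2 says of lymphocytes: "Once PEG-ADA is withdrawn, the numbers of circulating T, B, and NK lymphocytes will decline and may remain low for several months".

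A by-visit IgG table that mixes subjects on and off replacement therefore does not measure the patient's own antibody production. A patient still dependent on replacement can look recovered. A patient who has come off it can look worse.

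For dATP, deoxyadenosine and lymphocytes, the change score answers how the patient compares with their state on enzyme, if they were on enzyme at the baseline sample. A reader who sees a reduction in dATP, or a 12-month test of lymphocyte change, may assume that the reference is untreated disease. In a summary that also covers HSCT controls, a different mix of baseline enzyme use would shift one group's change relative to the other's, whatever the treatments did.

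**Working it through.** The plan gives no effect size or expected value for these endpoints, so there is no figure to reproduce. The check sets passages side by side and adds simple algebra.

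**1. Is status recorded, and is it used?** SAP 3 records PEG-ADA use and immunoglobulin status since the last visit, and has medication changes entered as a stop and a new start. The SAP uses the two therapies in treatment history (8.2.3), in event-free survival (8.3.1.2), in IgRT cessation (8.3.2.2) and in time to PEG-ADA withdrawal (8.3.3.1). None of these feeds the summaries at issue. The sensitivity analyses (8.3.4) concern major protocol violations only.

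**2. IgG.** Write measured IgG as own plus infused. The change from baseline b to visit v is then

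(own_v − own_b) + (infused_v − infused_b).

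| Baseline | Visit | Effect on apparent recovery |
|---|---|---|
| off IgRT | on IgRT | overstated by the infused part at the visit |
| on IgRT | off IgRT | understated by the infused part at baseline |
| on IgRT | on IgRT | either direction; own IgG not separable |
| off IgRT | off IgRT | no infused part |

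A baseline from diagnosis may precede IgRT (first row). In an infant it may also contain maternal immunoglobulin (Protocol 3.1.4.1), which pulls the change down. The levels, as opposed to the changes, are raised at every on-IgRT visit. The documents give no IgG levels or infused amounts, so no size follows.

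**3. Which post-infusion values are on PEG-ADA?** Take a month as 30 days and use the windows in Protocol 4.1 and 7.5.8.

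- Planned stop: 30 ± 6, days 24 to 36.
- Month-1 visit: 30 ± 5, days 25 to 35. Relative to the stop: 25 − 36 = −11 to 35 − 24 = +11 days.
- Six-week visit: 42 ± 5, days 37 to 47. Relative to the stop: 37 − 36 = 1 to 47 − 24 = 23 days after.
- Month-3 visit: 90 ± 14, from day 76, so at least 76 − 36 = 40 days after.

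Month 1 mixes on- and off-enzyme values. Week 6 may carry some enzyme, since Protocol 3.2.2 describes weekly dosing. Without a restart, later visits are off enzyme. The 6- and 12-month tests thus compare off-enzyme values with a baseline that is on enzyme for anyone then receiving PEG-ADA.

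**4. dATP, gene therapy against HSCT.** Let U be untreated dATP and E dATP on enzyme, the same in both groups. Let F_I and F_H be the final means, and p_I and p_H the shares on enzyme at baseline. Mean change is F − [pE + (1 − p)U], so the between-group difference is

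(F_I − F_H) + (p_I − p_H)(U − E).

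The second term reflects baseline enzyme use alone. With assumed shares 0.9 and 0.9 it is 0; with 0.9 and 0.5 it is 0.4 of (U − E); with 1.0 and 0 it is all of (U − E). Reversing the shares reverses the sign. Neither the shares nor patient dATP values are in the documents, so the actual size cannot be computed.

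**5. Restart of PEG-ADA.** Protocol 4.1 and 8.4 attach study withdrawal to a restart. Protocol 7.5.8 allows a restart and a later second stop without mentioning withdrawal, and the off-study list in 8.5 does not include restart. If such patients stay, on-enzyme values enter the late summaries. If they leave, later visits contain relatively more responders. The SAP says nothing on either case.

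**The case against.** The strongest reply is that the on-enzyme baseline is a fair clinical reference, fixed by the protocol's own PEG-ADA schedule, and mostly works against the product. Levels by visit and individual plots do not depend on baseline, and the lymphocyte and immunoglobulin plots carry age-related normal ranges. IgA and IgM are already summarised. Previous PEG-ADA is tabulated for gene-therapy subjects (SAP 8.2.3) and enzyme use before transplant for controls (8.2.15). The HSCT dATP summary is descriptive and conditional on data, and dATP is not among the HSCT comparisons listed in SAP 6. Most of this stands, and it limits the PEG-ADA part to labelling. It does not repair pooled IgG, and previous PEG-ADA use is not status at the baseline sample.

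Stronger readings that the documents do not support:

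- *That most baselines are known to be on enzyme.* Protocol 9.2.5 expects most patients to have received PEG-ADA, in a discussion of immunogenicity. It gives no count at the baseline sample.
- *That a dATP change score would misclassify successes.* In Protocol 3.2.4.4 dATP went up in a patient who stayed well off enzyme, and the increase is described as one "in the red blood cell dATP levels suggesting that the total mass of gene corrected lymphocytes producing ADA was not sufficient for systemic detoxification". The protocol reads that as a real metabolic shortfall.
- *That the lymphocyte understatement can be quantified.* The same section reports that in one patient "there was an overall 25% decrease in the total numbers of T cells and a decrease in the B and NK cell numbers", over two months. In the other patient T-cell counts rose.
- *That restarts or affected IgG readings can be forecast from earlier trials.* Protocol Table 1 shows 25 of 36 off enzyme; the remaining 11 are not a count of restarts. The five children in Protocol 3.2.5 who stopped immunoglobulin give no per-visit count for this trial.
- *That the controls lacked prior enzyme.* Protocol 3.2.2 describes other transplants, not this centre's cohort.

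**Conclusion.** The point holds in a limited form. The IgG part is the firmer: as written, SAP 8.3.2.2 lets infused product count within a primary endpoint, and the pooled change cannot be read as humoral recovery. The direction depends on IgRT status at both time points, so it should not be described as always favouring the product.

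The PEG-ADA part is an unlabelled reference state for dATP, deoxyadenosine and lymphocytes. It is probably conservative against untreated disease, because the protocol expects counts to fall and metabolites to rise without enzyme. The gene-therapy/HSCT dATP summary is open to a shift from baseline enzyme mix. That shift is zero if the groups have the same mix.

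None of these effects can be sized from the documents. The only firm figures are the timing ones: month 1 straddles the stop by up to 11 days each way, week 6 falls 1 to 23 days after it, and month 3 at least 40 days after it, for a 30-day month and no restart. Overall and event-free survival are unaffected. This is a minor-to-moderate correction, worth making because it is cheap.

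**What to change.** 1. **SAP 8.3.2.2.** Summarise IgG separately for visits on and off IgRT, with the number in each and the count of all treated subjects beside it. At on-IgRT visits rely on IgA and IgM for humoral recovery. Flag IgG baselines taken at diagnosis.
2. **SAP 8.3.1.4 and 8.3.1.5.** Tabulate PEG-ADA status at the baseline sample. Label the change scores and the 6- and 12-month tests accordingly. Mark on-enzyme values in tables and plots: month 1, possibly week 6, and any after a restart.
3. **Gene-therapy/HSCT dATP summary.** Show, or split by, enzyme status at baseline. Where a control's status is unknown, compare levels rather than changes.
4. **Definition.** State how long after the last PEG-ADA dose or immunoglobulin infusion a sample counts as on treatment, since the visit form records use since the last visit.
5. **Restart.** Reconcile Protocol 4.1 and 8.4 with 7.5.8 and 8.5 on whether a PEG-ADA restart means leaving the study. Then state in the SAP how post-restart values enter each summary. Which clinical rule applies is not a matter for this point.

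The cost is SAP wording, status flags and a few tables. The inputs are mostly planned already: status and medication dates in the schedule, and previous PEG-ADA for controls in Protocol Appendix 8. Some control dates were not recorded, so an unknown category is needed. With about 10 on-study subjects the cells will be very small, and off-treatment cells select responders, hence the full count beside them.
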